7.6 INVESTIGATIONAL STUDY DRUG ACCOUNTABILITY

ACP-196 capsules must be kept in a locked limited access room. The study drug must not be used outside the context of the protocol. Under no circumstances should the investigator or other site personnel supply ACP-196 capsules to other investigators, subjects, or clinics or allow supplies to be used other than as directed by this protocol without prior authorization from Acerta Pharma.

Study drug accountability records must be maintained and readily available for inspection by representatives of Acerta Pharma and are open to inspections by regulatory authorities at any time.

Each shipment of study drug will contain a Clinical Supplies Shipping Receipt Form (CSSF) that must be appended to the site's drug accountability records. Additionally a Drug Re-order Form for requesting more study drug is provided in the pharmacy binder. If it is used, then the Drug Re-order Form must also be included in the site's drug accountability records.

Contents of each shipment must be visually inspected to verify the quantity and document the condition of study drug capsules. Then the designated recipient completes and signs the CSSF. A copy of the signed CSSF must be faxed or emailed to Acerta Pharma at the fax number/emailing address listed on the form.

An Investigational Drug Accountability Log must be used for drug accountability. For accurate accountability, the following information must be noted when drug supplies are used during the study:

- 1. study identification number (ACE-MY-001)
- 2. subject identification number
- 3. lot number(s) of ACP-196 dispensed for that subject
- 4. date and quantity of drug dispensed
- 5. any unused drug returned by the subject

At study initiation, the monitor will evaluate and approve the site's procedure for investigational product disposal/destruction to ensure that it complies with Acerta Pharma's requirements. If the site cannot meet Acerta Pharma's requirements for disposal/destruction, arrangements will be made between the site and Acerta Pharma or its representative, for return of unused investigational product. Before disposal/destruction, final drug accountability and reconciliation must be performed by the monitor. All study supplies and associated documentation will be regularly reviewed and verified by the monitor.

7.7 RECORD RETENTION

The investigator and other appropriate study staff are responsible for maintaining all documentation relevant to the study. Mandatory documentation includes copies of study protocols and amendments, each FDA Form 1572, IRB/IEC approval letters, signed ICFs, drug accountability records, SAE forms transmitted to Acerta Pharma, subject files (source documentation) that substantiate entries in eCRFs, all relevant correspondence and other documents pertaining to the conduct of the study.

An investigator shall retain records for a period of at least 2 years after the date the last marketing application is approved for the drug for the indication for which it is being investigated; or, if no application is to be filed or if the application is not approved for such indication, until 2 years after the investigation is discontinued and regulatory authorities have been notified. The investigator must notify Acerta Pharma and obtain written approval from Acerta Pharma before destroying any clinical study records at any time. Acerta Pharma will inform the investigator of the date that study records may be destroyed or return to Acerta Pharma.

Acerta Pharma must be notified in advance of, and Acerta Pharma must provide express written approval of, any change in the maintenance of the foregoing documents if the investigator wishes to move study records to another location or assign responsibility for record retention to another party. If the investigator cannot guarantee the archiving requirements set forth herein at his or her study site for all such documents, special arrangements must be made between the investigator and Acerta Pharma to store such documents in sealed containers away from the study site so that they can be returned sealed to the investigator for audit purposes.

7.8 PROTOCOL AMENDMENTS

Acerta Pharma will initiate any change to the protocol in a protocol amendment document. The amendment will be submitted to the IRB/IEC together with, if applicable, a revised model ICF. If the change in any way increases the risk to the subject or changes the scope of the study, then written documentation of IRB/IEC approval must be received by Acerta Pharma before the amendment may take effect. Additionally under this circumstance, information on the increased risk and/or change in scope must be provided to subjects already actively participating in the study, and they must read, understand, and sign any revised ICF confirming willingness to remain in the trial.

7.9 PUBLICATION OF STUDY RESULTS

Acerta Pharma may use the results of this clinical study in registration documents for regulatory authorities in the United States or abroad. The results may also be used for papers, abstracts, posters or other material presented at scientific meetings or published in professional journals or as part of an academic thesis by an investigator. The study is being conducted as part of a multicenter clinical trial. Data from all study centers shall be pooled and analyzed for publication in a final report (Primary Publication). The investigator agrees that the Primary Publication, which will be coordinated by Acerta Pharma, will be the first publication to present the pooled study results. After the Primary Publication, or if the Primary Publication is not published within 1 year of termination of the study, the investigator may freely publish or present the results of his or her work conducted under the clinical trial agreement subject to providing Acerta Pharma with the opportunity to review the contents of any proposed presentation, abstract or publication about such work, including any results of this study, 90 days in advance of any presentation or submission for publication. Within that 90-day period, Acerta Pharma may review the proposed publication to identify patentable subject matter and/or any inadvertent disclosure of its confidential information, which must be redacted from any final publication or presentation. If necessary, to permit the preparation and filing of patent applications, Acerta Pharma may elect an additional review period not to exceed 60 days.

In most cases, the principal investigators at the sites with the highest accruals of eligible subjects, who have provided significant intellectual input into the study design, shall be listed as lead authors on manuscripts and reports of study results. The Medical Monitor, study director and/or lead statistician may also be included in the list of authors. This custom can be adjusted upon mutual agreement of the authors and Acerta Pharma.

7.10 CLINICAL TRIAL INSURANCE

Clinical trial insurance has been undertaken according to the laws of the countries where the study will be conducted. An insurance certificate will be made available to the participating sites at the time of study initiation.

7.11 GENERAL INVESTIGATOR RESPONSIBILITIES

The principal investigator must ensure that:

- 1. He or she will personally conduct or supervise the study.
- 2. His or her staff and all persons who assist in the conduct of the study clearly understand their responsibilities and have their names included in the Study Personnel Responsibility/Signature Log.
- 3. The study is conducted according to the protocol and all applicable regulations.
- 4. The protection of each subject's rights and welfare is maintained.
- 5. Signed and dated informed consent and, when applicable, permission to use protected health information are obtained from each subject before conducting nonstandard of care study procedures. If a subject or subject's legal guardian withdraws permission to use protected health information, the investigator will obtain a written request from the subject or subject's legal guardian and will ensure that no further data be collected from the subject.
- 6. The consent process is conducted in compliance with all applicable regulations and privacy acts.
- 7. The IRB/IEC complies with applicable regulations and conducts initial and ongoing reviews and approvals of the study.
- 8. Any amendment to the protocol is submitted promptly to the IRB/IEC.
- 9. Any significant protocol deviations are reported to Acerta Pharma and the IRB/IEC according to the guidelines at each study site.
- 10. Electronic CRF pages are completed within 5 days of each subject's visit (unless required earlier for SAE reporting).
- 11. All IND Safety Reports/ Suspected Unexpected Serious Adverse Reaction (SUSAR) Reports are submitted promptly to the IRB/IEC.
- 12. All SAEs are reported to Acerta Pharma Drug Safety/Designee within 24 hours of knowledge and to the IRB/IEC per their requirements.

8.0 REFERENCES

Bradshaw JM. The Src, Syk, and Tec family kinases: distinct types of molecular switches. Cell Signal 2010;22:1175-1184.

Appendix 1. Performance Status Scores

Grade	ECOG
0	Fully active, able to carry on all pre-disease performance without restriction
1	Restricted in physically strenuous activity but ambulatory and able to carry out work of a light or sedentary nature, eg, light house work, office work
2	Ambulatory and capable of all self-care but unable to carry out any work activities. Up and about more than 50% of waking hours
3	Capable of only limited self-care, confined to bed or chair more than 50% of waking hours
4	Completely disabled. Cannot carry on any self-care. Totally confined to bed or chair
5	Dead

As published in Am J Clin Oncol:

Credit: Eastern Cooperative Oncology Group Chair: [name]

Available at: http://www.ecog.org/general/perf_stat.html. Accessed 23 August 2013.

Appendix 2. Adverse Event Assessment of Causality

Is there a reasonable possibility that the event may have been caused by study drug?

No___Yes___

The descriptions provided below will help guide the principal investigator in making the decision to choose either "yes" or "no":

No = There is no reasonable possibility that the event may have been caused by study drug.

The adverse event:

- may be judged to be due to extraneous causes such as disease or environment or toxic factors
- may be judged to be due to the subject's clinical state or other therapy being administered
- is not biologically plausible
- does not reappear or worsen when study drug is re-administered
- does not follow a temporal sequence from administration of study drug

Yes = There is a reasonable possibility that the event may have been caused by study drug.

The adverse event:

- follows a temporal sequence from administration of study drug
- is a known response to the study drug based on clinical or preclinical data
- could not be explained by the known characteristics of the subject's clinical state, environmental or toxic factors, or other therapy administered to the subject
- disappears or decreases upon cessation or reduction of dose of study drug
- reappears or worsens when study drug is re-administered

Inhibitors			
Strong (≥5-fold Increase in AUC)	Moderate (2- to 5-fold Increase in AUC)	Weak (1.25- to <2-fold Increase in AUC)	
Boceprevir	Amprenavir	Alprazolam	
Chloramphenicol	Aprepitant	Amiodarone	
Clarithromycin	Atazanavir	Amlodipine	
Cobicistat	Ciprofloxacin	Atorvastatin	
Conivaptan	Darunavir	Bicalutamide	
Indinavir	Diltiazem	Buprenorphine	
Itraconazole	Erythromycin	Cilostazol	
Ketoconazole	Fluconazole	Cimetidine	
Lopinavir	Fosamprenavir	Cyclosporine	
Mibefradil	Grapefruit juice ¹	Fluoxetine	
Nefazodone	Imatinib	Fluvoxamine	
Nelfinavir	Verapamil	Ginkgo ¹	
Posaconazole		Goldenseal ¹	
Ritonavir		Isoniazid	
Saquinavir		Nilotinib	
Suboxone		Oral contraceptives	
Telaprevir		Ranitidine	
Telithromycin		Ranolazine	
Voriconazole		Tipranavir	
		Zileuton	
Inducers			
Strong (≥80%	Moderate (50 to 80%	Weak (20 to 50%	
Decrease in AUC)	Decrease in AUC)	Decrease in AUC)	
Avasimibe	Bosentan	Amprenavir	
Carbamazepine	Efavirenz	Aprepitant	
Phenytoin	Etravirine	Armodafinil	
Rifampin	Modafinil	Echinacea ¹	
St. John's wort ¹	Nafcillin	Pioglitazone	
		Prednisone	
		Rufinamide	
1. Food or herbal product			

Appendix 3 Inhibitors of CYP3A4

Primary reference: http://www.fda.gov/Drugs/DevelopmentApprovalProcess/DevelopmentResources/DrugInteractionsLabeling/ucm0 93664.htm

LTFU^q × Abbreviations: CR = complete remission; ECG = electrocardiogram, ECOG = Eastern Cooperative Oncology Group, Ig = immunoglobulin; mos = months; PE = Follow Up^c Days (± 2) × × × × × × × × × As clinically indicated or to Cycles 5-12^b Every 6 mos confirm a CR Every 2 mos Every 2 mos Days (± 2) 28 × × × × × \times × × × confirm a CR Days (± 2) clinically indicated Cycle 4 or to 28 As × × × × × × × × × × × Days (± 2) confirm a Cycle 3 ndicated clinically or to К As 28 × × × × × × × × × × × Bone Marrow Days (± 2) only Cycle 2 28 × × × × × × × × × × × × 15 × × × × × × × × 28 Ś × × × × × × × × × × × × × 22 × × × × × × × × × Days (± 2) Cycle 1 15 × × × × × × × × × × × ω Ĕ × × × × × × × × × × Ĕ × × × × × × × > × _ Screening^a × × × × × × × × × × × × × × Pharmacodynamics PE^d/Vital signs^e/Weight Study drug compliance **Pharmacokinetics**^o Time-to-next treatment T/B/NK cell count^k Serum chemistryⁱ Disease markers^I Urine pregnancy Tumor assessment^p Lab assessments: Informed consent Confirm eligibility Hematology^h (aspirate/biopsy) /Skeletal survey^p dexamethasone Adverse events Medical history Urinalysis^j Bone marrow ECOG status Concomitant medications dispensed test^g ACP-196/ Д С Ш

Appendix 4. Schedule of Assessments

physical exam; LTFU = long-term follow up

Confidential

Footnotes for ACE-MY-001 Schedule of Study Activities:

- Screening tests should be performed within 21 days before the first administration of study drug, unless otherwise indicated. a.
- Any subjects who have not progressed while receiving study drug treatment, may be eligible to enroll into a long-term follow up study and continue to receive ACP-196. ġ.
- The screening physical examination will include, at a minimum, the general appearance of the subject, height (screening only) and weight, and examination of the skin, A 30-day (± 7 days) safety follow-up visit is required when subjects discontinue study drug unless they start another anticancer therapy within that timeframe. ن ن ъ.
- eyes, ears, nose, throat, lungs, heart, abdomen, extremities, musculoskeletal system, lymphatic system, and nervous system. Symptom-directed physical exams are done thereafter.
 - Vital signs (blood pressure, pulse, respiratory rate, and temperature) will be assessed after the subject has rested in the sitting position. ي نە
- Subjects should be in supine position and resting for 2 10 minutes before study-related ECGs. 12-lead electrocardiogram (ECG) will be done in triplicate (2 1 minute apart) at screening. The calculated QTc average of the 3 ECGs must be ≤ 480 ms for eligibility.
 - Women of childbearing potential only. If positive, pregnancy must be ruled out by ultrasound to be eligible.
 - Hematology includes complete blood count with differential and platelet and reticulocyte counts. Cycle 1 Day 1 hematology does not need to be repeated if screening hematology was within 5 days. ъ.
- urea nitrogen (BUN), calcium, chloride, creatinine, C-terminal telopeptide, glucose, lactate dehydrogenase (LDH), magnesium, phosphate, potassium, sodium, total bilirubin. Serum chemistry: albumin, alkaline phosphatase, bone-specific alkaline phosphatase, alanine transaminase (ALT), aspartate aminotransferase (AST), bicarbonate, blood total protein, and uric acid. Cycle 1 Day 1 serum chemistry does not need to be repeated if screening hematology was within 5 days. .____
 - Urinalysis: pH, ketones, specific gravity, bilirubin, protein, blood, N-terminal telopeptide, and glucose.
 - (JB/NK cell count (ie, CD3, CD4, CD8, CD19, CD16/56). During Cycle 5-12, only done at end of Cycle 6 and 12.
 - Refer to Sectin 4.1 for a list of myeloma disease markers.
- Pharmacodynamic samples are drawn predose and 4 hours (±10 minutes) postdose on the days indicated. Note: These timepoints are relative to the morning dose. Ë
 - Pharmacodynamic samples are drawn predose on the days indicated. . ⊂ o
 - Pharmacokinetic samples are drawn per Table 4-1.
- Refer to Section 4-2. Bone marrow aspirate/biopsy and skeletal survey are required at baseline (ie, before the first dose of study drug). Thereafter they are required as indicated in the table above. d
- Subjects who discontinue study therapy will continue on study for follow-up of safety and time-to-next therapy for myeloma unless they withdraw consent for further follow-÷
- The indicated samples at this timepoint (Cycle 1 Day 1) must be drawn predose ۔

Confidential

## **TABLE OF ABBREVIATIONS**

AE(s)	adverse event(s)
Bid	twice per day
CBR	clinical benefit rate
CR	complete response
CSR	clinical study report
CTCAE	Common Terminology Criteria for Adverse Events
DCR	disease control rate
DOR	duration of response
ECOG	Eastern Cooperative Oncology Group
Ex-US	Excluding United States of America
Ig	immunoglobulin
IRC	independent review committee
IPD	important protocol deviation
ISS	International Staging System
MedDRA	Medical Dictionary for Regulatory Activities
MM	multiple myeloma
MR	minimal response
NCI	National Cancer Institute
PD	pharmacodynamics
PFS	progression-free survival
PK	pharmacokinetics
PR	partial response
PT	preferred term
SAE(s)	serious adverse event(s)
SAP	statistical analysis plan
sCR	stringent complete response
SD	stable disease
TEAE(s)	treatment-emergent adverse events
VGPR	very good partial response
WHO	World Health Organization

## **1. INTRODUCTION**

The purpose of this statistical analysis plan (SAP) is to provide details of the safety and efficacy analyses that have been outlined within Protocol Amendment 2 for Study ACE-MY-001, which is entitled “An Open-label, Phase 1b Study of ACP-196 in Subjects with Multiple Myeloma” dated January 13, 2016. The original SAP based on same protocol was for interim safety clinical study report (CSR) to support the new drug application (NDA) in relapsed and refractory mantle cell lymphoma. This SAP is updated to include efficacy analysis. Any change to the planned analyses described in the final SAP will be documented in the clinical study report (CSR).

Separate reports will be generated for pharmacokinetic (PK) and pharmacodynamic (PD) data.

From here on, acalabrutinib (generic name for formerly ACP-196) will be used in place of ACP-196 in this document.

## **2. OBJECTIVES**

### **2.1 Primary Objective**

- To characterize the safety profile of acalabrutinib with and without dexamethasone in subjects with relapsed or refractory (R/R) multiple myeloma (MM).

### **2.2 Secondary Objectives**

- To characterize the PK profile of acalabrutinib with and without dexamethasone and the PK profile of dexamethasone with concomitant acalabrutinib administration
- To evaluate the PD effects of acalabrutinib with and without dexamethasone
- To evaluate the activity of acalabrutinib with and without dexamethasone as measured by overall response rate (ORR), duration of response (DOR), clinical benefit rate, disease control rate, and progression-free survival (PFS).
- To explore the relationship between biological markers in MM cells and response to therapy

## **3. STUDY OVERVIEW**

### **3.1 Study Design**

This study is a multicenter, open-label, randomized, parallel-group study to be conducted at approximately 20 sites in 2 countries (United Kingdom and United States). Forty subjects are planned to be randomized 1:1 into the following 2 cohorts to receive acalabrutinib, with or without dexamethasone:

- Cohort 1 (acalabrutinib monotherapy): acalabrutinib 100 mg bid continuously
- Cohort 2 (acalabrutinib + dexamethasone): acalabrutinib 100 mg bid continuously and 40 mg dexamethasone once weekly

Due to limited evidence of efficacy of acalabrutinib monotherapy in R/R MM subjects in this study, in a memo dated March 15, 2016 to all study sites, the enrollment was discontinued immediately and subjects who were randomized to receive acalabrutinib monotherapy were permitted to crossover to receive acalabrutinib + dexamethasone treatment.

One cycle is defined as a 28-day study treatment period. Treatment may be continued until disease progression (PD) or an unacceptable drug-related toxicity occurs. All subjects who discontinue study drug will have a safety follow-up visit 30 ( $\pm 7$ ) days after the last dose of study drug unless they have started another cancer therapy within that timeframe.

All subjects will have hematology, serum chemistry, and urinalysis safety panels done at screening. Once dosing commences (Day 1), all subjects will be evaluated for safety, including serum chemistry, and hematology, once weekly for the first 4 weeks, every 2 weeks in Cycle 2 and monthly thereafter. PK/PD testing will be done in Cycle 1 and Cycle 2. The end of trial is defined as the point when the last subject on the study exits the study for any reason.

### **3.2 Sample Size**

The trial seeks to exclude an uninteresting ORR of  $\leq 15\%$  (i.e., the response rate that might be associated with single-agent dexamethasone therapy [Anderson 2013]) in favor a target response rate of  $\geq 40\%$ . Considering a sample size of 19 subjects per cohort, the power to detect the difference between a null hypothesis response rate of 15% and an alternative-hypothesis response rate of 40% with a 0.025 one-sided significance level is 69% using a one-group, exact binomial test. A sample size of 19 subjects per cohort

will also provide a 97.5% 1-sided confidence interval centered around an expected ORR of 40% that excludes an ORR of 18.6% as a lower bound.

#### **4. STUDY ENDPOINTS**

##### **4.1 Safety Endpoints**

The safety of acalabrutinib with and without dexamethasone will be characterized by the type, frequency, severity, and relationship to study drug(s) of any treatment-emergent adverse events (AEs) or incidence of abnormalities of laboratory tests; serious adverse events (SAEs); or AEs leading to dose modification/delay or discontinuation of study treatment.

##### **4.2 Efficacy Endpoints**

Assessments of acalabrutinib efficacy in this study will be based on the criteria of standardized tumor response and disease progression for MM ([Rajkumar 2011] and [Blade 1998]).

- Overall response rate (ORR)
- Duration of response (DOR)
- Clinical benefit rate (CBR)
- Disease control rate (DCR)
- Progression-free survival (PFS)

##### **4.3 Pharmacokinetic and Pharmacodynamic Parameters**

Refer to separate reports for PK and PD parameters.

#### **5. HYPOTHESES AND MULTIPLICITY**

No formal statistical hypotheses will be tested. The clinical hypotheses are that acalabrutinib monotherapy and acalabrutinib + dexamethasone is safety and effective in subjects with R/R MM.

#### **6. ANALYSIS SETS**

## **6.1 All-Treated Population**

All-treated population is defined as all enrolled subjects who receive  $\geq 1$  dose of any study drug. All-treated population will be used for evaluating the safety and efficacy unless otherwise specified.

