3.4.4 Enrollment and Randomization Procedures

Enrollment of a subject into the study will be performed according to the following procedure:

- Notify the sponsor when a clinically eligible subject is identified and is ready to screen, to ensure enrollment availability on the study.
- After the subject has signed and dated the Informed Consent Form (ICF), all screening procedures have been completed, and eligibility has been confirmed, the subject can be officially enrolled in the study.
- To enroll a subject, the study center will fax/email a completed Enrollment Confirmation Form to the sponsor. The enrollment date will be the date that the form is faxed/emailed to the sponsor.
- An Enrollment Confirmation Form will be completed and faxed/emailed to the study center by the sponsor within 24 hours.
- The Enrollment Confirmation Form will contain cohort allocation per the randomization scheme generated by the sponsor.

Treatment must begin within the screening window (Section 4.1) and after the site has received the cohort allocation from the sponsor. Study treatment is not blinded on this study.

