Subjects who discontinue study therapy will continue on study for safety (Section 4.3) unless they withdraw consent for further follow-up. Thus, all subjects receiving \geq 1 dose of study drug will be followed during the immediate posttherapy period unless the subject withdraws consent for such follow-up to be conducted. The date the subject is withdrawn from study treatment or from the study and the reason for discontinuation will be recorded and also should be described on the appropriate eCRF.

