5.3 DEFINITION OF ANALYSIS POPULATIONS

The following definitions will be used for the analysis populations:

- Safety population: All enrolled subjects who receive ≥ 1 dose of study drug.
- Intent-to-treat (ITT) population: All subjects who have been randomized.

The safety population will be used for evaluating the safety parameters in this study. The ITT population will be analyzed for efficacy parameters in this study.

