#### 10.7.2 Analysis Methods

The analysis of ORR, CBR, DCR, and PFS will be conducted on the All-treated Population. The analysis of DOR will be conducted on the subset of the All-treated Population who achieve sCR, CR, VGPR or PR as their best overall response.

ORR, CBR, DCR will be calculated and the corresponding 95% two-sided confidence intervals will be derived. DOR and PFS will be estimated using the Kaplan-Meier (KM) method. KM estimates with 95% CIs will be calculated for event time quartiles, including median. In addition, listings for DOR and PFS will be provided, including the reason for censoring.

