### 12. CHANGES FROM PROTOCOL-SPECIFIED ANALYSES

There is no major change from protocol-specified analyses.

Due to the fact that a very small number of subjects has responded to study treatment, there will not be an exploration of drug response and biological markers.

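### The SAP moves ORR, CBR, DCR and PFS from the protocol's ITT population to treated subjects only, and SAP Section 12 does not declare the change

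*SAP*

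**What the plan says.** Protocol 5.3 defines two sets. For subjects with at least one dose it says "The safety population will be used for evaluating the safety parameters in this study". For all randomised subjects it says "The ITT population will be analyzed for efficacy parameters in this study".

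The SAP presents itself as the detail behind Protocol Amendment 2, but its Section 6 defines a single analysis set: enrolled subjects with at least one dose of any study drug. In substance this is the protocol's safety population. SAP 6.1 states "All-treated population will be used for evaluating the safety and efficacy unless otherwise specified", and SAP 10.7.2 repeats the choice: "The analysis of ORR, CBR, DCR, and PFS will be conducted on the All-treated Population". DOR is analysed in the responders within that set. No ITT set or ITT analysis appears anywhere in the SAP.

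SAP Section 12 opens with "There is no major change from protocol-specified analyses" and then lists only the decision not to explore biomarkers against response. SAP 10.7.1 still measures PFS from randomisation.

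**The concern.** The two documents name different populations for four of the five efficacy endpoints, and the section meant to record such differences does not mention it. SAP Section 1 promises that the CSR will document departures from the final SAP. That does not cover a departure from the protocol already built into the SAP, so a CSR author who relied on Section 12 would report no change.

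The two sets need not coincide. Protocol 3.4.4 says "Treatment must begin within the screening window (Section 4.1) and after the site has received the cohort allocation from the sponsor". In this open-label trial a subject can therefore be randomised, learn the cohort and never start. Such a subject cannot be a responder, so leaving that subject out can only push ORR, CBR and DCR up, or leave a zero rate at zero.

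Disclosure also matters because of timing. SAP version 2.0 (September 2018) added the efficacy analysis, and its Section 11 shows it was written knowing that very few subjects had responded.

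**Working it through.** **1. Text side by side**

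| Item | Protocol 5.3 | SAP 6.1, 10.7.2 and 12 |
|---|---|---|
| Safety set | At least one dose | At least one dose (All-treated) |
| Set for ORR, CBR, DCR, PFS | All randomised (ITT) | At least one dose (All-treated) |
| Change declared | – | No; only the biomarker work is listed |

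The escape clause in SAP 6.1 does not help, because 10.7.2 specifies All-treated again.

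**2. The plan's own figure.** Protocol 5.2 gives 69% power for n = 19, 15% versus 40%, one-sided 0.025, exact binomial test. The smallest qualifying cut-off is 7 responders, with exact alpha 0.0163 and power 0.692, so the figure reproduces. It is not affected by this point.

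**3. Effect on the rates.** Let N be the number randomised in a cohort, u the number never dosed and x the positive count (x > 0). An undosed subject contributes nothing to x, so

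(All-treated rate) / (ITT rate) = [x/(N-u)] / [x/N] = N/(N-u).

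| N | u = 1 | u = 2 |
|---|---|---|
| 20 (planned) | 20/19: +5.3% | 20/18: +11.1% |
| 12 (assumed) | 12/11: +9.1% | 12/10: +20.0% |

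N = 12 is an assumption. SAP 3.1 says "the enrollment was discontinued immediately" but does not give the number reached.

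**4. Illustrations with exact (Clopper-Pearson) 95% intervals.** All counts are assumed; the documents give none.

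| Endpoint | ITT | All-treated |
|---|---|---|
| ORR, u = 1 | 2/20 = 10.0% (1.2–31.7%) | 2/19 = 10.5% (1.3–33.1%) |
| ORR, u = 2 | 2/20 = 10.0% (1.2–31.7%) | 2/18 = 11.1% (1.4–34.7%) |
| ORR, u = 2 | 3/20 = 15.0% (3.2–37.9%) | 3/18 = 16.7% (3.6–41.4%) |
| ORR, u = 2 | 2/12 = 16.7% (2.1–48.4%) | 2/10 = 20.0% (2.5–55.6%) |
| DCR, u = 2 | 10/20 = 50.0% (27.2–72.8%) | 10/18 = 55.6% (30.8–78.5%) |

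**5. PFS.** An undosed subject censored at time 0 changes the Kaplan-Meier curve by exactly 0. If instead one undosed subject has the first event, the ITT curve is (N-1)/N times the All-treated curve from then on: 19/20 = 0.95, or 11/12 = 0.917. That event would probably not be captured, because Protocol 3.8 specifies follow-up only for subjects with at least one "dose of study drug will be followed during the immediate posttherapy period unless the subject withdraws consent".

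**6. DOR.** The responders are the same people in both sets, so nothing changes.

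**The case against.** The strongest reply is that no effect has been shown. The documents report no undosed subject. Allocation comes only after screening is complete and eligibility confirmed, the sponsor answers within 24 hours, and treatment must start inside the screening window, so a gap is possible but not likely to be large. This stands, and the effect is zero if nobody was undosed.

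The absolute shifts are also small. With 2 responders of 20 they are 0.5 to 1.1 percentage points against an interval about 30 points wide. With no responders in a cohort, ORR is 0% either way. Efficacy is secondary, SAP Section 5 tests no hypothesis, and Protocol 5.2 disclaims a formal comparison of the regimens. All of this limits the severity.

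Protocol 3.4.3 allows replacement of subjects who do not complete Cycle 2, so the contrast might be 21 randomised against 20 dosed (21/20, +5.0%) or 22 against 20 (+10.0%). The same formula covers this.

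SAP 10.2 summarises disposition for all enrolled subjects, and Protocol 5.1 calls for analyses by regimen and overall, so undosed counts by cohort may be recoverable. That makes a by-cohort row a clarification; it does not correct the efficacy denominators.

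Finally, the SAP names its set openly, and whether the change is major is a matter of judgement. But a section that lists a dropped exploratory analysis and omits a new population for four efficacy endpoints is not an accurate account. Nothing in either document reconciles the two texts.

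**Conclusion.** The concern holds. The SAP departs from Protocol 5.3 on the population for ORR, CBR, DCR and PFS, defines no ITT set, and leaves the departure out of Section 12. The direction is known: reported response rates equal or exceed the ITT rates. The size depends on the undosed count, which the documents do not give. It is nil for none, and at the planned 20 per cohort it is +5.3% relative for one and +11.1% for two. The larger figures at N = 12 rest on an assumed cohort size. PFS is in practice a labelling matter. No test or formal comparison depends on this, so it is a change that should be made, not one that threatens the trial's conclusions.

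**What to change.** In SAP Section 6, define the protocol's ITT population (all randomised, by assigned cohort), and use it in 10.7.2 for ORR, CBR, DCR and PFS, counting undosed subjects as non-responders. Keep All-treated for safety and as supportive efficacy. Two small edits follow:

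- In 14.3, censor PFS at randomisation when there is no adequate post-baseline assessment. The present rule uses the first-dose date, which an undosed subject does not have.
- In 10.2, report the number randomised but not dosed, by cohort.

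If the sponsor prefers All-treated as the main efficacy set, correct Section 12 to list the change of population with a reason. If everyone randomised was dosed, one sentence stating that closes the point.

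The cost is SAP wording and one disposition row. Reported rates may come out slightly lower.
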